The primary treatment for BCLM remains chemo-therapy and, more recently, targeted immunotherapy. Liver metastases from other primary tumors, such as colorectal cancers, are routinely resected as part of standard management. Breast cancer rarely develops isolated liver metastases because neo-plastic cells at this stage have often already reached systemic circulation with the possibility of further localization, unlike colon cancer, where the liver, through the portal system, is the first organ to be colonized. Therefore, the role of liver resection in BCLM remains controversial [6-8].

Hepatic resection and/or ablation was not associated with a survival advantage in some studies [9], whilst in other disclosed a remarkable improvement as compared to systemic treatment alone [10,11], thus indicating surgical intervention as suggested in highly selected patients with the goal of providing time off of systemic chemotherapy.

Our study thus aims to provide further insights in this complex and still unclear field of research.

OBJECTIVES

Primary Objective

Primary aim of the study is to compare the efficacy of liver resection vs. medical therapy alone in Breast Cancer Liver Metastasis (BCLM) patients.

Secondary Objectives

- To assess the recurrence rate after liver resection or medical treatment alone;
- To assess Recurrence free survival (RFS);
- To assess potential factors involved in both overall survival and RFS.

METHODS

Study design

Multicenter observational ambispective study.

Population

We will enroll all patients with BCLM underwent liver resection or medical treatment alone afferent to the Fondazione Policlinico Gemelli IRCSS of Rome (Italy), and other 8 International centers (as detailed in the attached document), following the inclusion and exclusion criteria hereafter detailed.

Study duration

The study will overall last 68 months since the approval of the present protocol by the sponsor center institutional review board (IRB), i.e. Fondazione Policlinico Gemelli IRCSS of Rome (Italy), and of all the satellite centers. The prospective enrolment of patients will last till the December 31, 2023 and follow-up phase will last for other 5 years, till December 31, 2028.

Study phases

The study foresees two distinct phases:

- **I phase (only retrospective phase)** → it will cover all patients underwent to either medical treatment or surgery for which all data are available, with a follow up of 5 years at March 31, 2023. We will retrieve all patients data from January 1994 till March 31, 2018. At the end of “phase I”, we foresee an “ad interim” analysis.
- **II phase (ambispective)** → we will further include all patients retrieved from the archives between April 1, 2018 and the April 30, 2023, as well as all prospectively enrolled patients till December 31 2023, so that the last patient enrolled will end the 5-years follow-up phase within December 31, 2028.

Inclusion criteria

- Age >18 years old;
- Presence of BCLM;
- BCLM and extra-hepatic disease;
- Any treatment;
- Ability to understand and sign the informed consent.

Exclusion criteria

- Inability to provide the informed consent;
- Patients who underwent Best Supportive Care or palliation.

Variables and procedures

The following data will be retrieved from medical archives of each participating center for all retrospectively enrolled patient.

Prospectively enrolled patients' data will instead be collected in the related medical record and reported, alongside all other patients' data, in an electronic dataset protected by password and accessible only to the PI and the co-investigators, and to any other person authorized by PI.

In depth, the following data will be included:

- Anonymized ID;
- Demographic and anthropometric data (e.g., age, sex, BMI, etc..);
- Name of the participating center;
- ER, PR and HER2 status,
- Presence of BRCA1-2 mutation,
- Neoadjuvant-radiotherapy,
- Neoadjuvant endocrine therapy,
- Neoadjuvant-chemotherapy,
- Neoadjuvant-anti-HER2,
- Date of breast surgery,
- Breast tumor T and N,
- Adjuvant radiotherapy,

- Ad-endocrine therapy, Ad-chemotherapy, and Ad-anti-HER2,
- Date of liver metastasis diagnosis,
- Date of liver surgery,
- Liver surgery,
- Liver resection major/minor (Segmental or wedge resection or Left Lateral),
- R status,
- Number of liver metastasis,
- Size of the bigger lesion (mm),
- Distribution (uni or bilobar),
- Postoperative morbidity,
- Hormone receptor expression in the liver metastasis (ER+, PR+),
- Extra-hepatic disease,
- Site of Extra-hepatic disease,
- Mortality and cause;
- Date of death or last FU observation,
- Recurrences,
- Site of recurrences,
- Date of recurrences.

ENDPOINTS

Primary endpoint

The primary endpoint is to analyze the efficacy of liver surgery as compared to medical therapy alone in terms of 5-years overall survival in patients with breast cancer who underwent to liver resection or medical therapy alone.

Secondary endpoints

- Recurrence rate;
- Post-operative mortality (in patients who underwent to surgical treatment).
- Post-operative complication (in patients who underwent to surgical treatment).
- To assess potential predictive factors of 5-years overall survival in patients with breast cancer who underwent to either liver resection or medical therapy alone.
- To assess recurrence free survival (RFS) of liver surgery as compared to medical therapy alone in terms of 5-years overall survival in patients with breast cancer who underwent to liver resection or medical therapy alone.
- To assess potential predictive factors of 5-years RFS in patients with breast cancer who underwent to either liver resection or medical therapy alone.

STATISTICAL ANALYSIS PLAN

Sample size calculation

The sample size was computed based on the assessment of an improvement in the OS of patients surgically treated as compared to systemic therapy alone.

Based on the evidence from Ruiz and colleagues [10], which reported a 5-years OS of 24% among women treated only with medical therapy and of 69% among those surgically treated, we hypothesize to obtain in our study sample an OS of 60% in the treated group and of 25% in the systemic therapy group.

As such, considering a treatment/control ratio of 0.15/0.85, a two-sided log-rank test with an overall sample size of 117 subjects (99 in the systemic therapy group and 18 in the surgical treatment group) achieves 90% power at a 0,05 significance level to detect a hazard ratio of 0,37 when the proportion of 5-year OS in the control group is 25%. The study will consider a time-window of 30 years of total enrolment (from 1994 to 2023) and a follow-up period of 5 years, for a total time of 35 years. The accrual pattern across time periods is uniform (all periods equal). We expect no subjects drop out both in the control group and treatment groups. The expect no. of events is of 96,5 in the control group and 14,3 in the treatment group. The sample size calculation was performed with PASS2022 v22.0.3 [12,13]. Such sample size estimation is consistent with the disease specific metastasis prevalence and on the no. of involved centers. In fact, we overall expect to include in both retrospective and

prospective phase 75-80 patients/center, for overall sample of 675-720 patients. Particularly, the retrospective phase, which will include patients till 2017 will consist of about 500 patients, already consistent with the sample size estimate provided, whilst the other will pertain to the period 2018-2023.

Statistical analysis

The sample will be described in its clinical and demographic characteristics by descriptive statistics techniques. In depth, qualitative data will be expressed as absolute and relative percentage frequency, whilst quantitative variables either by mean and standard deviation (SD) or median and interquartile range (IQR), as appropriate. To verify the Gaussian distribution of quantitative variables, the Shapiro-Wilk test will be applied.

Missing values, as <5% in all cases, were treated by *imputeR* package, using multiple imputation with Lasso Regression methods centered on the mean as for quantitative data, whilst classification trees for imputation by “rpartC” function, centered on the mode, i.e. most represented class object, were applied on qualitative data [14].

Between groups differences were analyzed by either the Chi squared test or the Fisher-Freeman-Halton test for qualitative data, whilst either the Student’s t test or non-parametric Mann-Withney U test will be applied on quantitative data, as appropriate.

Differences between groups will be further exemplified by clustered violin plots or plots describing pre-post variation in individual groups. Such plots will be produced with the R packages “ggplot2”, “ggstatsplot”, “ggpubr”, “ggprism”, and “ggsignif” [15-19].

OS will be calculated from the date of treatment initiation through the date of death from any cause; subjects alive at the last follow-up will be censored. Overall survival and RFS probabilities at 5 years will be estimated using the Kaplan Meier method and compared by the log-rank test. The KM curve will also be reported. The analysis will be performed with the R package “*ggplot2*” and “*survminer*” R packages [15,20].

To assess potential prognostic factors of 5-year RFS and OS, both univariable and multivariable Cox proportional hazards regression models will be fitted, and hazard ratios (HR) and 95% confidence intervals (CI) consequently reported. The proportionality of the hazards will be assessed by visual inspection of the hazards and Schoenfeld residuals. In case of doubtful proportionality, Cox weighted regression models will be fitted. “*survival*” and “*coxphw*” R packages will be used for the whole analysis [21-24]. The predictors to be included in the multivariable model will be selected on the basis of univariable analysis ($p < 0.05$ or suggestive, i.e. $0.05 \leq p < 0.10$) and expert opinion, also considering the possibility of overcoming the rule of 10 events per variable (EPV) [25,26]. Statistical significance will be set at a p-value < 0.05 . Suggestive p-values will be further reported ($0.05 \leq p < 0.10$). All analyses will be performed with R software version 4.2.0 (CRAN ®, R Core 2022) [27].

References

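### The surgical group is defined mainly by a resection that took place, with no place for patients operated on but not resected, so 5-year OS after surgery is likely overstated

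*Protocol*

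**What the plan says.** Two sets of wording in the protocol bear on who is in the surgical group.

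**Narrow: a resection was done.** Population enrols "all patients with BCLM underwent liver resection or medical treatment alone". The Primary Objective is to "compare the efficacy of liver resection vs. medical therapy alone". The Primary endpoint names the effect more widely, "analyze the efficacy of liver surgery as compared to medical therapy alone in terms of 5-years overall survival", but the same sentence closes on "patients with breast cancer who underwent to liver resection or medical therapy alone".

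**Broad: an operation or any treatment.** Under Study phases, phase I takes "all patients underwent to either medical treatment or surgery for which all data are available". The Inclusion criteria list "Any treatment". Under Secondary endpoints, post-operative mortality and complications are assessed in those treated surgically, with no mention of resection.

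The Variables and procedures list has liver surgery and its date as items of their own, then "Liver resection major/minor (Segmental or wedge resection or Left Lateral" and R status. No item marks a resection that was planned and abandoned. R status is recorded but not restricted, so incomplete resections are not excluded. No section says whether a patient operated on but not resected is excluded, kept in the surgical group or counted as medical therapy alone.

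**The concern.** Whether a resection takes place is settled only at the operation. A patient found at surgery to have more disease than imaging showed is not resected and, under the narrow wording, drops out of the surgical group. The medical group passes through no such filter: patients with equally unresectable disease that nobody has explored stay in it. The two groups are then not comparable even for the protocol's own question of resection against medical therapy alone. Part of any survival difference would come from the filter, even if resection had no effect.

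The planned log-rank test and Cox models cannot repair this, because the missing patients are not in the data. In a retrospective extraction reaching back to January 1994 across the sponsor's centre and eight others, a status that is not collected cannot be recovered at analysis. Because the wording differs between sections, centres could also apply different rules.

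**Working it through.** **1. The plan's own figures (Sample size calculation).** Inputs: 5-year OS 60% surgical and 25% systemic, split 0.15/0.85, N = 117, uniform accrual over 30 years, 5 further years of follow-up, no dropout.

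- HR = ln(0.60)/ln(0.25) = 0.368. The plan states 0.37.
- With exponential survival, the probability of an event is 0.96995 (control) and 0.81337 (surgical).
- Expected events: 117 × 0.85 × 0.96995 = 96.5 and 117 × 0.15 × 0.81337 = 14.3. Both match the plan.

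**2. How many patients could be affected.** The plan expects 675-720 patients. At 15% surgical, 0.15 × 675 = 101 and 0.15 × 720 = 108 resected. If a share *a* of attempts is abandoned, the number abandoned is n × a/(1 − a). The range a = 5-15% is an assumption.

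- a = 5%, n = 101.25: 101.25 × 0.05/0.95 = 5.3
- a = 15%, n = 108: 108 × 0.15/0.85 = 19.1

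So about 5 to 19 patients.

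**3. Effect on 5-year OS.** Take 60% for resected patients (the plan's figure). For abandoned attempts take 25%, which is the plan's figure for systemic therapy and is borrowed here as an assumption. Then OS of all operated = 0.60(1 − a) + 0.25a, and HR = ln(OS)/ln(0.25).

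| Abandoned | OS of all operated | Overstatement | HR |
|---|---|---|---|
| 5% | 58.3% | 1.8 points | 0.39 |
| 10% | 56.5% | 3.5 points | 0.41 |
| 15% | 54.8% | 5.3 points | 0.43 |

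The HR column keeps the plan's convention of converting 5-year OS as if hazards were proportional. It is a guide only.

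**4. Sensitivity to the borrowed 25%.** If no patient with an abandoned resection survived 5 years, OS of all operated would be 57.0%, 54.0% and 51.0% for a = 5%, 10% and 15%, with HR 0.41, 0.44 and 0.49. If these patients did as well as resected patients, there would be no overstatement.

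**5. Effect on the medical group if they were moved there.** At 25% OS the shift is zero, because that is the comparator's own value. In the extreme case of 19 patients with 0% survival added to 0.85 × 720 = 612, OS is 0.25 × 612/631 = 24.2%, a shift of 0.8 points.

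**6. Effect on power.** In log-rank simulations with 574 medical and 101 surgical patients, power stayed at about 100% for surgical OS from 58% down to 48%. The issue is bias in the estimate, not the ability to detect a difference.

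**The case against.** The strongest reply is that the protocol asks about resected patients. The Primary Objective says so, and the primary endpoint's own sentence ends on resection, so surgery and resection look like two words for one group. On that view the survival of resected patients is simply what it is. As a description of resected patients, that stands. As a comparison it does not, because the medical group has not been through the same filter.

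Other parts of the reply hold, and they limit the point:

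- A reader might infer that the protocol firmly restricts the surgical group to completed resections. It does not: the phase I and inclusion wording is broader. The accurate finding is an unreconciled definition with no rule for these patients.
- A reader might infer that post-operative mortality and complications necessarily lose these operations from their denominator. Those endpoints already refer to surgically treated patients; the wording is only out of step with Population.
- Liver surgery is listed separately from extent of resection, so a record with an operation and no resection type might hint at an abandoned attempt. That is an inference from a blank, not a recorded status.
- A reader might infer that the comparator is lowered. Step 5 of the working shows nothing material, and a patient who had an operation does not plainly fit medical therapy alone.

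It can also be said that handling of aborted procedures belongs in a statistical analysis plan or case report form, neither of which is shown. But the protocol itself fixes who is enrolled, how the groups are formed and which variables are extracted, and it does so inconsistently.

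**Conclusion.** The point holds as a gap and inconsistency in the group definition, with a likely direction of bias. If patients operated on but not resected are left out, and if they do worse than resected patients, 5-year OS after surgery is overstated by about 2 to 5 points and the hazard ratio reads 0.37 where 0.39-0.43 would apply. This rests on two assumptions that the documents do not supply: 5-15% of attempts abandoned, and 25% 5-year OS in those patients. The documents therefore do not support stating the overstatement as an established fact or giving it a firm size. Nor do they support a materially lowered comparator. The bias is moderate and would not by itself overturn an effect as large as the one planned for, but it cannot be corrected later if the status is not collected.

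**What to change.** - Use one definition of the surgical group in Population, Study phases, Inclusion criteria and Endpoints: all patients operated on with intent to resect liver metastases.
- Add one field beside the liver surgery item: resection completed, or attempted and abandoned.
- State that patients with an abandoned attempt are not counted as medical therapy alone.
- Report 5-year OS by attempted resection alongside completed resections. Where older records are incomplete, prespecify the attempted-resection analysis at least as a sensitivity analysis. Whether it should replace the primary comparison outright is more debatable, and the point does not depend on it.
- Use all operated patients as the denominator for post-operative mortality and complications.

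Cost: a few sentences, one field and some extra record review. The review means checking operating lists as well as resection records, which will be harder for the early years at nine centres. The surgical survival figure may come out slightly less favourable.

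### Phase I is restricted to patients with all data available while Phase II is not; if sites apply this as written, it can select on record completeness and bias 5-year OS

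*Protocol*

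**What the plan says.** All references are to the protocol.

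- **Phase I entry (Methods, Study phases).** Phase I covers patients "for which all data are available, with a follow up of 5 years at March 31, 2023". The retrieval window is stated next: "We will retrieve all patients data from January 1994 till March 31, 2018". An interim analysis follows at the end of this phase.
- **Phase II entry (same section).** "we will further include all patients retrieved from the archives between April 1, 2018 and the April 30, 2023", together with prospectively enrolled patients up to the end of 2023, "so that the last patient enrolled will end the 5-years follow-up phase within December 31, 2028". No completeness condition is attached.
- **Population and eligibility criteria (Methods).** The Population paragraph enrols every BCLM patient treated by resection or medical therapy at the participating centres, subject to the listed criteria. Those criteria mention neither completeness of data nor length of follow-up.
- **Variables and procedures.** The outcome item collected is "Date of death or last FU observation".
- **Statistical analysis.** For OS, "subjects alive at the last follow-up will be censored". For missing data, "Missing values, as <5% in all cases, were treated by" imputation.
- **Sample size calculation.** About 500 patients are expected from the retrospective phase and 675-720 overall. Five-year OS is assumed to be 25% with systemic therapy and 60% with surgery, and no drop-out is expected.

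**The concern.** The completeness condition is an explicit entry rule for the larger part of the sample and is absent for the rest, yet the two parts are counted together. It does not fit the text around it. If only complete records enter Phase I, there is nothing to impute there; if imputation is needed, the rule is not being followed. A site also cannot tell which fields count as all data, or whether a patient lost to follow-up at year 2 enters.

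This matters because completeness of an archive record can be related to outcome. A patient who died at year 2 has a closed survival record. A patient last seen alive at year 2 has no known 5-year status and could be set aside as incomplete. Conversely, an early death with a thin file could be set aside too. If this happens to different degrees in surgical and medical patients, the primary comparison is distorted. Regression on the patients who did enter cannot restore those who did not.

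**Working it through.** **1. Share of the sample affected.** 500/720 = 69% and 500/675 = 74%. The Sample size section describes the 500 as patients up to 2017, slightly short of the Phase I cut-off of March 31, 2018, so the share is approximate.

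**2. What the five-year clause means.** March 31, 2018 plus 5 years is March 31, 2023, exactly the date in the clause. Phase II is built the same way: December 31, 2023 plus 5 years is December 31, 2028. Both read as potential (calendar) follow-up. Potential follow-up does not depend on outcome, so on this reading the clause adds no bias and OS stays at 25% and 60%.

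**3. The plan's own hazard ratio.** HR = ln(0.60)/ln(0.25) = 0.511/1.386 = 0.368. The stated 0.37 is reproduced.

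**4. If patients lost alive before 5 years are excluded.** Assumptions: exponential survival at the protocol's OS values, loss independent of death, and only patients with known 5-year status kept. The loss rates are mine; the protocol gives none.

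- λ = -ln(S₅)/5, which is 0.2773 (medical) and 0.1022 (surgical).
- A = P(followed alive to 5 years) = exp(-5(λ+μ)).
- B = P(death observed) = λ/(λ+μ) × (1 - A).
- Apparent 5-year OS = A/(A+B).

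Medical, μ = 0.10: A = 0.152, B = 0.623, OS = 0.152/0.775 = 19.6%.
Surgical, μ = 0.03: A = 0.516, B = 0.374, OS = 0.516/0.890 = 58.0%.
Apparent HR = ln(0.580)/ln(0.196) = 0.33.

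Losses reversed: medical 0.215/0.923 = 23.3%, surgical 0.364/0.685 = 53.1%, HR = ln(0.531)/ln(0.233) = 0.43.

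No true effect (both arms 40%), first loss pattern: 33.1% medical and 37.9% surgical, HR = ln(0.379)/ln(0.331) = 0.88.

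These HRs are ratios of log 5-year survival, not fitted Cox estimates.

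**5. Sensitivity to the assumed loss.** Here loss is an annual probability p, so that A = S₅(1-p)⁵.

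| Annual loss, medical / surgical | OS medical / surgical | HR |
|---|---|---|
| 0 / 0 | 25% / 60% | 0.37 |
| 2% / 2% | 23.9% / 58.7% | 0.37 |
| 5% / 5% | 22.1% / 56.6% | 0.38 |
| 10% / 10% | 19.3% / 52.7% | 0.39 |
| 10% / 0 | 19.3% / 60% | 0.31 |
| 0 / 10% | 25% / 52.7% | 0.46 |

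Equal loss lowers OS by about 1 to 7 points but hardly moves the HR. Unequal loss moves the HR in either direction.

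**6. If incomplete early deaths are excluded instead.** With a fraction d of deaths before 5 years dropped, OS = S₅/(S₅ + (1-d)(1-S₅)). For d = 10%: 0.25/0.925 = 27.0% and 0.60/0.96 = 62.5%. For d = 30%: 0.25/0.775 = 32.3% and 0.60/0.88 = 68.2%. OS now moves up, so the direction depends on who is dropped.

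**The case against.** The strongest reply is that the sentence is loosely worded and that the rest of the protocol shows what is meant. Much of this stands.

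- **Five years actually survived.** A reader might infer that entry requires five observed years, which would drop every early death and make 5-year OS 100%. The documents rule this out: death dates are collected, OS of 25% and 60% is planned, and the calendar dates match exactly.
- **Conflict with censoring.** A reader might infer that the censoring rule contradicts the entry rule. It does not. Patients alive after a full five years must still be censored, and the rule serves Phase II as well. If anything, it suggests that patients alive at last contact are meant to stay in.
- **Every listed field complete.** A reader might infer that a record missing any item is excluded, with heavy attrition. The variable list cannot bear this. Date of liver surgery, R status, extent of resection and postoperative morbidity do not exist for medically treated patients, so a literal reading would remove the whole control group, planned at 85%.
- **Assumed inputs.** The protocol expects no drop-out, and at zero loss the effect in step 4 is zero. The loss rates and the arm difference are illustrative.

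What the reply does not remove is the completeness clause itself. It is explicit, applies to Phase I only, leaves open which data it means, and does not depend on how the five years are read. No other sentence says that patients lost before five years are retained.

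**Conclusion.** The point holds as a defect in the entry rule that can bias the primary result, not as a demonstrated bias. The completeness restriction covers about 69-74% of the expected sample and the interim analysis, is absent from Phase II, and conflicts with the Population paragraph and the imputation plan. The five-year clause, read as potential follow-up, is harmless but should say so.

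Size and direction are unknown. Under the assumptions shown, apparent HRs run from 0.31 to 0.46 around a true 0.37 when loss differs by arm, and stay at 0.37-0.39 when it is equal. OS falls if patients lost alive are dropped and rises if incomplete early deaths are dropped. This is a moderate point, but it should be settled before archive extraction, because excluded patients cannot be recovered in the analysis.

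**What to change.** Replace the Phase I rule with: *all consecutive eligible patients whose treatment for BCLM began between January 1994 and March 31, 2018 (at least 5 years of potential follow-up by March 31, 2023), regardless of data completeness, death or loss to follow-up.* Censor lost patients at last contact, as the Statistical analysis section already provides, handle missing covariates by imputation, and state the same consecutive-patient rule for Phase II.

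When making this change, check it against the inclusion criterion "Ability to understand and sign the informed consent", which as worded makes no exception for archive patients who have died. That is a separate matter and is not part of the sizes given here.

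The cost is one sentence in the protocol plus retrieval of incomplete archive records. The downside is small: more missing data to handle and some censoring before 5 years.

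### The extra-hepatic inclusion item, as written, shuts out liver-only patients; read as probably meant, it leaves disease extent in the medical arm unlimited for an unadjusted survival comparison

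*Protocol*

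**What the plan says.** - **Rationale (text before Objectives).** After describing conflicting studies, the Protocol concludes for the favourable ones: "thus indicating surgical intervention as suggested in highly selected patients". It also calls isolated liver metastases rare in breast cancer, without a figure.
- **Population.** "We will enroll all patients with BCLM underwent liver resection or medical treatment alone", at the sponsor's centre and eight others.
- **Inclusion criteria.** Separate items include "Presence of BCLM", "BCLM and extra-hepatic disease" and "Any treatment". Nothing says that any of them are alternatives.
- **Exclusion criteria.** Apart from inability to consent, the only exclusion is "Patients who underwent Best Supportive Care or palliation".
- **Variables and procedures.** Number of liver metastases, size of the largest, lobar distribution, and presence and site of extra-hepatic disease are all recorded.
- **Sample size calculation.** Planning rests on a published study "which reported a 5-years OS of 24% among women treated only with medical therapy and of 69% among those surgically treated". Its title in the reference list calls it a case-matched comparison. The Protocol plans on 60% against 25%, with 15% of patients in the surgical group.
- **Statistical analysis.** OS is estimated by Kaplan-Meier and compared by the log-rank test, with no adjustment. Cox models are planned for prognostic factors, with predictors chosen by univariable p-value and expert opinion. No matching, weighting or restriction is stated.

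**The concern.** There are two linked problems.

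First, an eligibility rule has to be applied the same way at nine centres, partly in archives going back to 1994. A centre that follows the list literally drops liver-only patients, and a centre that follows the Population paragraph keeps them. Case mix could then differ by centre for reasons of wording alone.

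Second, the primary aim is to compare the efficacy of resection with that of medical therapy alone. That contrast is informative among patients whose disease extent occurs in both groups. If the medical group also contains patients with more extensive disease than any resected patient, the unadjusted curves mix the effect of surgery with the effect of disease burden. Where no resected patient has a given extent, a regression model can only extrapolate, so the choice of comparison population matters as well as the choice of covariates.

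**Working it through.** **1. The criterion against the rest of the Protocol**

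| Place | If extra-hepatic disease is mandatory | If it is optional |
|---|---|---|
| Population paragraph (all patients with liver metastases) | Contradicted | Consistent |
| Item requiring liver metastases | Redundant | Needed |
| Extra-hepatic disease as a collected variable | Constant | Informative |
| The item itself, in a list where all must be met | Consistent | Needs words that are not there |

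Three places favour the optional reading and only the literal wording of the item favours the other. The text is wrong as written, and the intention is probably permissive.

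**2. What limits the medical group on the permissive reading**

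The item on treatment sets no limit. Best supportive care and palliation are excluded, which removes some patients with advanced disease. No criterion refers to number, size, distribution or extra-hepatic spread.

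**3. The Protocol's planning figures**

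The planned hazard ratio is ln(0.60)/ln(0.25) = (−0.511)/(−1.386) = 0.368, which agrees with the stated 0.37. With exponential survival, uniform accrual over 30 years, 5 further years of follow-up and a 0.15/0.85 split of 117, the expected events come to 96.5 and 14.3, as stated. These figures are not in dispute.

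**4. Illustration of what disease extent alone can do**

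Assumptions, none of them from the Protocol: surgery has no effect; surgical patients and comparable medical patients share 5-year OS *s*; the remaining medical patients have 5-year OS *u*; and these make up a fraction *f* of the medical group.

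- Medical-group OS: *m* = (1 − *f*)·*s* + *f*·*u*
- Apparent 5-year cumulative-hazard ratio: ln(*s*)/ln(*m*)

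| *s* | *u* | *f* | *m* | Ratio |
|---|---|---|---|---|
| 0.40 | 0.10 | 0.30 | 0.31 | 0.916/1.171 = 0.78 |
| 0.40 | 0.10 | 0.50 | 0.25 | 0.916/1.386 = 0.66 |
| 0.40 | 0.10 | 0.70 | 0.19 | 0.916/1.661 = 0.55 |
| 0.30 | 0.20 | 0.30 | 0.27 | 1.204/1.309 = 0.92 |

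A mixture of exponentials has no constant hazard ratio, so these are ratios of cumulative hazard at five years and not Cox estimates.

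**5. How often the unadjusted log-rank test would then favour surgery**

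This was simulated with a 15/85 split, follow-up cut at 5 years and 2,000 runs per case. The nominal rate in that direction is 2.5%.

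| Case (*s*, *u*, *f*) | N = 117 | N = 700 |
|---|---|---|
| 0.40, 0.10, 0.30 | about 10% | about 49% |
| 0.40, 0.10, 0.50 | about 25% | about 92% |
| 0.40, 0.10, 0.70 | about 48% | over 99% |
| 0.30, 0.20, 0.30 | about 4% | about 8% |

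The expected 675 to 720 patients do not protect against this. A larger sample makes a false difference more likely to reach significance.

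**The case against.** The strongest reply is that the literal reading is one the Protocol itself rules out, so the first half is a one-line correction. That largely stands. A reader might infer that liver-only patients will in fact be excluded, or that the study will miss its target population. The documents do not support this: the Population paragraph and the variable list point the other way, and the objective is not confined to liver-only disease.

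A reader might also infer that the medical group will be filled with patients who could never be resected. The documents do not support that either. They give no proportion, they nowhere say that extra-hepatic disease precludes resection, the criterion applies to both groups, and palliative patients are excluded. What can be said is that disease extent in the medical group is not limited.

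It is further argued that broad eligibility is legitimate in an observational cohort, that the disease-extent variables are recorded so overlap can be examined later, and that a separate analysis plan may deal with it. The first two are right, and for that reason the cohort need not be narrowed. The third does not dispose of the point: the Protocol has its own statistical analysis plan section, and that section states the OS comparison as an unadjusted log-rank test.

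Finally, the survival rates in the illustration are invented, and the case that lands on the Protocol's 25% does so by choice of inputs. That is correct. The figures show direction and possible size only, and lack of overlap is a possibility that has not been demonstrated in data.

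**Conclusion.** The point holds in two parts. The contradiction between the inclusion item, the Population paragraph and the collected variables is established from the text and needs no assumption. The comparability weakness follows from three stated facts taken together: no limit on disease extent among medically treated patients, surgery described as reserved for selected patients, and an unadjusted comparison of OS.

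Its size cannot be read from the Protocol. With no true surgical effect, the assumed cases give 5-year cumulative-hazard ratios from about 0.92 to 0.55. These depend entirely on the assumed survival rates and on the share of non-comparable medical patients. None reaches the planned 0.37, so the illustration does not show that the hypothesised effect would be an artefact. It does show that a statistically significant result could arise without any benefit of surgery.

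**What to change.** 1. Reconcile the Population paragraph and the inclusion list, so that one item admits patients with liver metastases from breast cancer, with or without extra-hepatic disease.
2. Keep the broad cohort. Pre-state that the primary surgery-versus-medical comparison is made in patients within the overlap of disease extent, defined by number of metastases, largest size, uni- or bilobar distribution, and presence and site of extra-hepatic disease. The rule could be the ranges seen in resected patients or a region of propensity overlap. It should be set without reference to outcome and before the interim analysis planned at the end of phase I; if that analysis has already been run, say so.
3. Report the unrestricted log-rank comparison as secondary, and show results by extra-hepatic status.
4. Restate power for the resulting allocation.

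**Cost.** No new data are needed. The primary comparison will have fewer medical patients and a narrower target population. At the planned 15% share, the expected cohort holds about 0.15 × 675 = 101 to 0.15 × 720 = 108 surgical patients, against 18 in the sample size calculation, so there is probably room. A reader should not take 675 to 720 against 117 as proof of this: the 117 applies only to a hazard ratio of 0.37 at a 0.15/0.85 split, and restriction changes the split and may bring the effect closer to 1.
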